9.4 Data Analysis Conventions

All data analysis will be performed by SDC after the study is completed and the database has been locked and released for unmasking. Statistical programming and analyses will be performed using SAS® Version 9.4.

Quantitative variables will be summarized using descriptive statistics including the number of observations (n), mean, standard deviation (SD), median, minimum, and maximum values. Means, medians, and confidence intervals (CI) will be reported to two decimal places and SDs to three. Summaries for discrete variables will include frequency counts and percentages. All percentages will be rounded to one decimal place (i.e., XX.X%). Differences between the active treatment group and placebo will be calculated as Active minus Placebo and change from baseline will be calculated as follow-up visit minus baseline.

All efficacy analyses will be 2-sided at a significance level of 0.10. CIs for differences between treatment groups will be two-sided at 90% confidence. All p-values will be rounded to four decimal places; p-values less than 0.0001 will be presented as "<0.0001"; p-values greater than 0.9999 will be presented as ">0.9999".

All summaries will be presented by treatment group. Summaries of data from the Comfort Assessment and Safety and Efficacy Assessment of the study will be summarized separately. Summaries will be provided for demographics, baseline medical history, concurrent therapies, and subject disposition.

For the purpose of summarization, the following will be coded to the Medical Dictionary for Regulatory Activities (MedDRA) and World Health Organization (WHO) Drug Dictionary Enhanced (DDE), as appropriate: medical history, concurrent therapies, and AEs.

9.5 Adjustments for Multiplicity

There will be no adjustments for multiple endpoints or multiple treatment comparisons for this early phase, exploratory study.

10. Disposition of Subjects

Subject disposition will be presented in terms of the numbers and percentages of subjects who were randomized, completed the study, and discontinued from the study. Subjects who are not discontinued from the study will be considered study completers. Disposition will be summarized by treatment group and for all subjects.

The number and percentage of subjects discontinued from the study and the reasons for study discontinuation will be summarized by treatment group for all randomized subjects. The reasons for study discontinuation that will be summarized include: AEs, protocol violations, administrative reasons, sponsor termination of study, subject choice, and other. A subject listing will be provided that includes the date of and reason for premature study discontinuation.

The number and percentage of subjects with protocol deviations will be summarized by treatment group for all randomized subjects. A subject listing will be provided that includes the date of the deviation, the deviation description and the classification of whether the deviation was judged to be major or minor.

In addition, subject listings will be provided that include informed consent date, inclusion and exclusion criteria violations, and exclusions from the PP population.

11. Demographic and Baseline Variables

11.1 Demographic Variables

The demographic variables collected in this study include age, gender, race, ethnicity and iris color. Subjects who record more than one race will be grouped into a single category denoted as multi-racial.

Age (years) will be summarized, overall and by treatment, using continuous descriptive statistics. Age will also be categorized as follows: <65 years and ≥ 65 years. Age will be reported in years and calculated using the following formula:

$$\text{Age} = (\text{informed consent date} - \text{date of birth}) / 365.25 \text{ truncated as an integer}$$

The number and percentage of subjects will be presented, overall and by treatment, for age category, gender, race, ethnicity and iris color. Percentages will be based on the total number of subjects in each treatment group except for iris color, which will be based on the total number of eyes in each treatment group. A subject listing that includes all demographic variables will be provided.

11.2 Baseline Variables

Baseline worst dry eye symptoms, duration of dry eye syndrome and OSDI© will be summarized and listed.

12. Medical History and Concomitant Medications

12.1 Medical History

Medical history will be summarized using discrete summary statistics and presented by treatment group at the subject and event level by system organ class (SOC) and preferred term (PT). If a subject reports the same PT multiple times within the same SOC, that PT will only be reported once within that SOC. As with the PT, if a subject reports multiple conditions within the same SOC, then that SOC will only be reported once. Separate tables will be created for ocular and non-ocular medical history. Medical history will be coded using MedDRA, version 20.0. The summaries will be based on the mITT population.

Listings of medical history will be generated separately for ocular and non-ocular data.

12.2 Prior and Concomitant Medications

At the first screening visit, subjects will be asked what medications they are taking, as well as those the subject may have taken prior to Visit 1b. At each study visit, subjects will be asked what concomitant medications they are currently taking or if there have been any changes to their medication since their first visit.

All prior and concomitant ocular and non-ocular medications will be listed using the mITT population including generic name, route of administration, start date, stop date, dosage, and indication. Prior and concomitant medications will be coded using the WHO DDE version B2, September 2016, to the appropriate Anatomical Therapeutic Chemical (ATC) classification and WHO generic term.

Counts and percentages of ocular and non-ocular concomitant medications will be summarized separately using WHO Drug ATC classification and preferred name. Summaries will be displayed by treatment group and for all subjects. Subjects with multiple medications in the same ATC class or preferred name will be counted only once for that respective ATC class or preferred name.

13. Dosing Compliance and Treatment Exposure

13.1 Dosing Compliance

Dosing compliance (% compliance) will be assessed by calculating the number of actual doses received and comparing that to the number of expected doses as follows:

$$\text{Compliance (\%)} = \frac{\text{Number of Actual Doses Received}}{\text{Number of Expected Doses}}$$

Number of Expected Doses x 100%

The number of actual doses received will be calculated from the used and unused bottles recorded in the eCRF. The number of expected doses that will be used for calculating compliance will be calculated as $\{3 \times [\text{date of last dose} - \text{date of Visit 2 (Day 1)}]\} + 3$ for all subjects, regardless of study completion status.

A categorical dosing compliance variable will also be derived as non-compliant (<80%), compliant ($\geq 80\%$ and $\leq 114\%$) and over compliant ($>114\%$).

Treatment compliance (%) will be summarized for the Safety population using continuous descriptive statistics. The compliance categories defined above will be summarized with counts and percentages.

A subject listing of compliance will also be produced.

13.2 Treatment Exposure

For the Safety and Efficacy Assessment, extent of exposure will be calculated in days using the following:

Extent of Exposure (days) = [Date of last dose – Date of Visit 2b (Day 1)] + 1

Extent of treatment exposure (days) for each subject exposed to study drug will be summarized with continuous descriptive statistics for each treatment group, using the Safety population. A subject listing of treatment exposure will also be produced.

14. Safety Analyses

Frequencies and percentages of subjects with treatment-emergent adverse events (TEAEs), serious TEAEs, and TEAEs causing discontinuation will be provided by treatment group. An AE is treatment emergent if it occurs or worsens after the first dose of study treatment. Furthermore, frequencies will be given of subjects with TEAEs by SOC and PT; by SOC, PT and maximal severity; by SOC and PT for treatment-related AEs; by SOC, PT for SAEs; and by SOC, PT, and time of onset. Separate summaries will be provided for ocular specific and all AEs (including systemic).

Other safety endpoints including VA, slit-lamp biomicroscopy, corneal sensitivity, undilated fundoscopy, IOP (non-contact), and vital signs will be summarized by treatment group, visit, and time point (where relevant) using descriptive statistics. Changes or shifts from baseline will also be summarized where appropriate. For assessments performed by eye, study eye and fellow eye will be summarized separately. In addition, shifts from baseline to worst on-treatment value for ocular safety assessments will be summarized.

Safety variables will be summarized as appropriate. All safety analyses will be performed on the Safety population. No statistical inferential testing will be performed for safety variables.

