### 3 CLINICAL HYPOTHESES

The clinical hypotheses for this study are that TOP1630 Ophthalmic Solution has an acceptable safety and toleration profile compared to placebo and demonstrates clinically meaningful differences on signs and symptoms in subjects with dry eye syndrome.

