mmHg	Millimeters of Mercury
OD	Right Eye
OPI	Ocular Protection Index
OS	Left Eye
OSDI [®]	Ocular Surface Disease Index
OU	Both Eyes
OTC	Over-the-counter
PMNs	Polymorphonuclear Leucocytes
PP	Per Protocol
PT	Preferred Term
TID	Three Times a Day
SAE	Serious Adverse Event
SAP	Statistical Analysis Plan
SDC	Statistics and Data Corporation
SOC	System Organ Class
SOP	Standard Operating Procedure
TFBUT/TBUT	Tear Film Break-up Time
TEAE	Treatment Emergent Adverse Event
VA	Visual Acuity
VAS	Visual Analogue Scale
WHO	World Health Organization

1. Introduction

The purpose of this statistical analysis plan (SAP) is to describe the planned analyses and reporting for protocol TOP1630-TV-04, version 2.0 dated 20Jan2017.

This SAP is being written with due consideration of the recommendations outlined in the most recent International Conference on Harmonization (ICH) E9 Guideline entitled Guidance for Industry: Statistical Principles for Clinical Trials and the most recent ICH E3 Guideline, entitled Guidance for Industry: Structure and Content of Clinical Study Reports (CSR).

This SAP describes the data that will be analyzed and the subject characteristics, efficacy, and safety assessments that will be evaluated. This SAP provides details of the specific statistical methods that will be used. The statistical analysis methods presented in this document will supersede the statistical analysis methods described in the clinical protocol. If additional analyses are required to supplement the planned analyses described in this SAP they may be completed and will be identified in the CSR.

2. Study Objectives

The primary objective of this study is to compare the safety and tolerability of TOP1630 Ophthalmic Solution to placebo. The secondary objectives are to compare the efficacy of TOP1630 Ophthalmic Solution to placebo for the treatment of the signs and symptoms of dry eye syndrome.

3. Study Variables

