5.2 Masking and Unmasking

This is a double-masked study. Subjects, investigators and site staff, the sponsor and Ora/Statistics & Data Corporation (SDC) staff are masked to the treatment group assignments during the randomization process and for the duration of the study.

Under normal circumstances, the mask should not be broken. When medically necessary, an investigator may need to determine what treatment has been assigned to a subject. The investigator will contact Ora/Sponsor with the details of the emergency unmasking request. Ora/Sponsor will make the final determination if the unmasking request will be granted. If granted, the investigator will complete unmasking via the "scratch-off" label affixed to the subject's source documents. If the unmasking label is not available, unmasking information may be provided by the Unmasked designees [REDACTED] [REDACTED]). The investigator must also indicate in source documents and in the eCRF that the mask was broken and provide the date, time, and reason for breaking the mask. Subjects should have their study drug discontinued immediately if treatment assignment is unmasked.

The overall randomization code will be broken only for reporting purposes. This will occur once all final clinical data have been entered into the database, data queries have been resolved, and assignment of subjects to the analysis populations has been completed. The database will be kept masked until after the database lock has occurred.

6. Sample Size and Power Considerations

The study is not powered to show statistical differences for any of the efficacy endpoints. The sample size was determined based on prior clinical trial experience in subjects with dry eye syndrome and is deemed to be robust sufficient to evaluate the safety and tolerability of TOP1630 Ophthalmic Solution in this population and to gather efficacy data that will aid in powering future clinical trials.

With a sample size of 60 subjects in the Safety and Efficacy Assessment, the study will have 79% probability of detecting AEs occurring at a rate of 5% or more in either treatment arm.

7. Data Preparation

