An overall tabular summary of AEs will be presented that includes the number of events and the number and percentage of subjects who experienced at least one event, by treatment group and overall. This summary will also include breakdowns of AEs further categorized as ocular or non-ocular, SAEs, AEs by maximal severity, AEs leading to subject withdrawal and AEs resulting in death. Additional summaries of AEs will be provided showing the number and percentage of subjects who experienced at least one AE, separately for ocular and non-ocular AEs. Ocular and non-ocular AEs will be summarized separately using discrete summary statistics and presented by treatment group at the subject and event level by SOC and PT using the Safety population. If a subject reports the same PT multiple times within the same SOC, that PT will only be reported once within that SOC. As with the PT,

if a subject reports multiple conditions within the same SOC, that SOC will only be reported once. The occurrence of AEs suspected to be related to IP will also be tabulated by SOC and PT, separately for ocular and non-ocular events. SAEs will also be summarized separately for ocular and non-ocular events. All AEs will be presented in a listing.

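### Comparing safety with placebo is part of the primary objective, but adverse events get only counts and percentages, with no between-arm difference or interval

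*SAP*

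**What the plan says.** SAP 2 sets a comparative aim: "The primary objective of this study is to compare the safety and tolerability of TOP1630 Ophthalmic Solution to placebo". Protocol 3 words the clinical hypothesis the same way, namely that "TOP1630 Ophthalmic Solution has an acceptable safety and toleration profile compared to placebo".

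The AE analysis is in SAP 14 and 14.1. SAP 14 opens: "Frequencies and percentages of subjects with treatment-emergent adverse events (TEAEs), serious TEAEs, and TEAEs causing discontinuation will be provided by treatment group". SAP 14.1 describes the overall summary (Table 14.3.1.1) as containing "the number of events and the number and percentage of subjects who experienced at least one event, by treatment group and overall". It splits this by ocular and non-ocular, seriousness, maximal severity, withdrawal and death. Further tables go by system organ class and preferred term, and by suspected relationship to study drug. SAP 14 also states: "No statistical inferential testing will be performed for safety variables". Neither section, nor the list of safety tables in SAP 21, names a risk difference, a ratio or an interval for AEs.

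Three other places bear on the point:

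- SAP 9.4 fixes a direction, "Differences between the active treatment group and placebo will be calculated as Active minus Placebo", and a level, "CIs for differences between treatment groups will be two-sided at 90% confidence". It attaches neither to an AE output.
- SAP 6 gives the only quantitative safety statement about the sample size: a "79% probability of detecting AEs occurring at a rate of 5% or more in either treatment arm".
- SAP 15 compares drop comfort between arms with two-sample t-tests. SAP 3.1 lists drop comfort as a safety variable.

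**The concern.** The objective asks how TOP1630 compares with placebo. For AEs the plan answers with each arm's figures side by side and leaves the comparison to the reader. Two percentages do not show how uncertain their difference is. With about 30 subjects per arm, matching percentages could mean that the drug adds little, or that the trial is too small to show what it adds. The planned tables do not separate these two cases.

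The 79% does not help. It concerns whether an event would be seen at all in one arm, not how large an excess over placebo the data would leave open. Protocol 1 describes this as the first administration of TOP1630 in man, so the AE comparison will probably be read closely when later studies are planned.

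**Working it through.** **Inputs.** Planned arm size is 30 active and 30 placebo (SAP 4.1). The interval level is 90%, two-sided (SAP 9.4). The documents give no AE rates, so every event count below is an assumption chosen to show a range.

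**1. The plan's own figure.** The probability of at least one event in n subjects with true rate p is 1 − (1 − p)^n.

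- n = 30, p = 0.05: 1 − 0.95^30 = 0.785, which reproduces the 79%.
- n = 60, p = 0.05: 1 − 0.95^60 = 0.954, which does not.

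The 79% is therefore a single-arm probability of seeing one or more events. Placebo does not enter the calculation.

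**2. Interval for the difference.** For each arm take the Wilson limits (l, u) at z = 1.645. With d = p1 − p2, where 1 is TOP1630 and 2 is placebo, the Newcombe limits are

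- lower = d − √[(p1 − l1)² + (u2 − p2)²]
- upper = d + √[(u1 − p1)² + (p2 − l2)²]

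The 90% Wilson limits with n = 30 are 0 to 0.083 for 0/30, 0.041 to 0.226 for 3/30, and 0.107 to 0.343 for 6/30.

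Worked case, 6 v 3, with d = 0.20 − 0.10 = 0.10:

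- lower = 0.10 − √(0.093² + 0.126²) = 0.10 − 0.156 = −0.056
- upper = 0.10 + √(0.143² + 0.059²) = 0.10 + 0.154 = +0.254

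| Assumed subjects with event, TOP1630 v placebo | Difference (points) | 90% Newcombe CI (points) | 95% Newcombe CI (points) |
|---|---|---|---|
| 0 v 0 | 0 | −8.3 to +8.3 | −11.4 to +11.4 |
| 3 v 3 | 0 | −13.9 to +13.9 | −16.9 to +16.9 |
| 6 v 6 | 0 | −17.0 to +17.0 | −20.2 to +20.2 |
| 6 v 3 | +10 | −5.6 to +25.4 | −8.8 to +28.5 |

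The Miettinen-Nurminen score interval at 90% is close: −13.6 to +14.0 for 3 v 3, −16.9 to +17.2 for 6 v 6, and −5.6 to +25.7 for 6 v 3. It could not be computed for 0 v 0 with the software used. The choice between the two methods does not drive the result.

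**3. An arm with no events.** The exact one-sided 95% upper bound for 0/30 solves (1 − p)^30 = 0.05, so p = 1 − 0.05^(1/30) = 0.095, or 9.5%.

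**The case against.** The case for leaving the plan alone has real substance.

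- **The choice is deliberate and usual.** The SAP openly rules out inferential testing of safety variables, and descriptive AE reporting is normal in an early exploratory study of this size. That stands as an argument against tests. It does not argue against an estimate with an interval, which needs no p-value.
- **The counts determine the intervals.** Any reader can compute them, and SAP 1 allows supplementary analyses identified in the study report. That is true, so no data are lost. But the AE categories and the interval method would then be chosen after unmasking.
- **The AE tables are fuller than two columns of percentages.** This stands. There are event counts, an overall column, and splits by severity, seriousness and relatedness. None of these is a between-arm estimate.

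A reader might also draw stronger conclusions, which the documents do not support:

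- That the primary objective gets no comparison and all inference is on efficacy. SAP 15 applies t-tests to drop comfort, which belongs to the tolerability side of that objective.
- That the SAP breaks its own rule in 9.4. The interval sentence directly follows the sentence on the efficacy significance level and is most naturally read as an efficacy convention.
- That the plan sets out to claim equivalence with placebo. The hypothesis speaks of an acceptable profile, and no margin or non-inferiority claim appears.
- That the sample size is wrong. The plan claims no power for a difference in AEs.

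**Conclusion.** The point holds for AEs. The plan sets a comparative safety objective but schedules no between-arm AE difference or interval, and its one quantitative safety figure is not a comparison. If observed counts are equal, the 90% interval still reaches an excess on TOP1630 of about 8 points with no events in either arm, 14 points at 10% per arm and 17 points at 20% per arm. If TOP1630 shows twice the placebo percentage (20% v 10%), the interval runs from −5.6 to +25.4 points.

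These sizes rest on 30 evaluable subjects per arm and on assumed counts. Fewer subjects in the safety population would widen the intervals. This is a worthwhile reporting improvement. It does not correct an invalid analysis and does not call the design into question.

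**What to change.** Prespecify in SAP 14.1 the TOP1630 minus placebo risk difference, with a two-sided 90% Newcombe interval, for four categories:

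1. any AE (Table 14.3.1.1);
2. any ocular AE (Table 14.3.1.1);
3. any AE leading to withdrawal (Table 14.3.1.1);
4. any ocular AE suspected to be related to study drug. Put this in Table 14.3.1.4 or in a new row of Table 14.3.1.1, because the overall summary as described has no relatedness breakdown.

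Where an arm has no events in a category, also give the exact one-sided 95% upper bound for that arm's rate (9.5% for 0/30). Label all of this as estimation without p-values, so that the statement ruling out inferential testing can stand for AEs.

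The cost is a short addition to SAP 14.1 and a few table rows. Sample size, data collection and conduct are unchanged. The drawback is that the intervals will be wide and will make the safety statement look less favourable than bare percentages would.

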14.1 Adverse Events

An AE is defined as any untoward medical occurrence associated with the use of an investigational product (IP) in humans, whether or not considered IP-related. TEAEs are defined as AEs that occur after the first use of IP. Per the protocol, only AEs that begin or worsen after receipt of the first dose of IP will be captured in the database for this study; therefore, TEAEs and AEs are equivalent in this study and will be denoted as AEs. All AEs will be assigned a severity grade of mild, moderate, or severe. Their relationship to IP will be classified as suspected (definite, probable or possible) or not suspected (not related). The expectedness of an AE will be classified as unexpected, expected or not applicable. Documentation of AEs will include onset date, severity, action(s) taken, IP relationship, expectedness, outcome, resolution date, and seriousness. All AEs will be coded using MedDRA classifications with reference to SOCs and PTs (MedDRA version 20.0).

An adverse event is considered serious if, in the view of either the investigator or sponsor, it results in any of the following outcomes:

- Death;
- A life-threatening AE;
- Inpatient hospitalization or prolongation of existing hospitalization;
- A persistent or significant incapacity or substantial disruption of the ability to conduct normal life functions;
- A congenital anomaly/birth defect.

Important medical events that may not result in death, be life-threatening, or require hospitalization may be considered serious when, based upon appropriate medical judgment, they may jeopardize the subject and may require medical or surgical intervention to prevent one of the outcomes listed above.

An overall tabular summary of AEs will be presented that includes the number of events and the number and percentage of subjects who experienced at least one event, by treatment group and overall. This summary will also include breakdowns of AEs further categorized as ocular or non-ocular, SAEs, AEs by maximal severity, AEs leading to subject withdrawal and AEs resulting in death. Additional summaries of AEs will be provided showing the number and percentage of subjects who experienced at least one AE, separately for ocular and non-ocular AEs. Ocular and non-ocular AEs will be summarized separately using discrete summary statistics and presented by treatment group at the subject and event level by SOC and PT using the Safety population. If a subject reports the same PT multiple times within the same SOC, that PT will only be reported once within that SOC. As with the PT,

if a subject reports multiple conditions within the same SOC, that SOC will only be reported once. The occurrence of AEs suspected to be related to IP will also be tabulated by SOC and PT, separately for ocular and non-ocular events. SAEs will also be summarized separately for ocular and non-ocular events. All AEs will be presented in a listing.

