# **9 ADVERSE EVENTS**

## **9.1 Adverse Event**

An adverse event is defined as any untoward medical occurrence associated with the use of a drug in humans, whether or not the event is considered drug-related. An adverse event can therefore be any unfavorable and unintended sign (e.g., an abnormal laboratory finding), symptom, or disease occurring after the subject started

dosing with the study drug, without any judgment about causality. Any pre-existing medical condition that worsens after administration of the study drug will also be considered a new adverse event.

Collection of Adverse Events will begin at the time of informed consent.

If there is a worsening of a medical condition that was present prior to the administration of the informed consent, this should also be considered a new adverse event and reported. Any medical condition present prior to the administration of the study drug that remains unchanged or improved should not be recorded as an adverse event at subsequent visits.

Study drug includes the investigational drug under evaluation, placebo, or any other medications required by the protocol given during any stage of the study.

Documentation regarding the adverse event should be made as to the nature, date of onset, end date, severity, relationship to study drug, action(s) taken, seriousness, and outcome of any sign or symptom observed by the physician or reported by the subject upon indirect questioning.

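### SAP 14.1 equates AEs with TEAEs on the false premise that the protocol captures only post-dose events, so pre-dose AEs could enter the by-arm tables

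*SAP*

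**What the plan says.** SAP 14.1 states the premise: "Per the protocol, only AEs that begin or worsen after receipt of the first dose of IP will be captured in the database". From that alone it concludes "therefore, TEAEs and AEs are equivalent in this study and will be denoted as AEs". Its short definition of treatment emergence is "TEAEs are defined as AEs that occur after the first use of IP". The reporting that follows is of AEs, by treatment group: "An overall tabular summary of AEs will be presented that includes the number of events and the number and percentage of subjects". The AE table titles, 14.3.1.1 to 14.3.1.7, likewise name adverse events and carry no treatment-emergent restriction.

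The introduction to SAP 14 keeps AEs and TEAEs apart and asks for TEAE frequencies: "An AE is treatment emergent if it occurs or worsens after the first dose of study treatment". Protocol 10.4.5 uses the same definition.

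On collection, protocol 9.1 says "Collection of Adverse Events will begin at the time of informed consent". It also makes worsening of a condition present before consent reportable. The section is not wholly consistent, because its AE definition speaks of events arising once dosing with study drug has begun. It then defines that term broadly: "Study drug includes the investigational drug under evaluation, placebo, or any other medications required by the protocol given during any stage of the study".

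SAP 18 declares no departure from the protocol's analyses.

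**The concern.** The SAP attributes to the protocol a capture rule that the protocol's explicit statement on collection contradicts, and uses it to drop the treatment-emergent filter. Comparing safety and tolerability with placebo is the primary objective, and these are its AE tables. Events before the first randomised dose cannot be caused by the assigned treatment. Counting them by arm raises incidence in both arms and, where there is a true excess on active, pulls the ratio towards 1, so that active looks more like placebo.

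**Working it through.** **Step 1: the plan's own AE figure.** Protocol 10.3 and SAP 6 give a 79% probability of detecting an AE with a 5% rate. With 30 subjects per arm, 1 − 0.95^30 = 0.785, which reproduces it. The figure is not in dispute. It is the only AE rate in either document, and it is a planning threshold, not an expected rate.

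**Step 2: the texts on timing and capture.**

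| Source | Content |
|---|---|
| Protocol 9.1 | Collection starts at consent (Visit 1b, Day −7 ± 1) |
| Protocol 8.3.1 and Appendix 1 | AE queries before and after CAE at each of Visits 1b, 2b, 3b and 4b: 8 in all |
| Protocol 7.1.2 and 8.3.1 | Randomisation and first randomised dose at the end of Visit 2b, listed after that visit's second AE query |
| Protocol 8.3.1 (early termination) and 9.3 | All AEs go to the source document and CRF/eCRF |
| Protocol 11.6 | Source data are transcribed to the eCRF; only screen failures are not entered |

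So 4 of 8 AE queries, and 2 of 4 CAE challenges, precede the first randomised dose. Nothing in the protocol keeps the resulting AEs of randomised subjects out of the database.

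**Step 3: what follows.** The documents do not show how the eCRF was built.
- eCRF built to the protocol and SAP 14.1 applied: AEs from consent onward enter the by-arm tables.
- eCRF built to SAP 14.1: the tables are clean, but the database omits AEs that the protocol requires.

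**Step 4: size, by illustration.** The run-in is 7/(7 + 28) = 20% of follow-up; the ± 1 day window gives 6/34 = 18% to 8/36 = 22%. Everything else is assumed: a constant hazard, 28-day placebo risk p, hazard ratio HR during treatment, and no extra AEs from the CAE challenges.

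λ = −ln(1 − p)/28

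TEAE-only risk = 1 − exp(−28·HR·λ)

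Risk with run-in counted = 1 − exp(−(7 + 28·HR)·λ), with HR = 1 on placebo

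For p = 20% and HR = 2:

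| | Active | Placebo | Risk ratio | Risk difference |
|---|---|---|---|---|
| TEAEs only | 1 − 0.8^2 = 36.0% | 20.0% | 1.80 | 16.0 points |
| Run-in counted | 1 − 0.8^2.25 = 39.5% | 1 − 0.8^1.25 = 24.3% | 1.62 | 15.1 points |

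Subjects added: 30 × (0.395 − 0.360) ≈ 1.0 on active and 30 × (0.243 − 0.200) = 1.3 on placebo, about 2.3 of 60. The risk difference is multiplied by (1 − p)^0.25 = 0.946, whatever the HR. Event counts, which SAP 14.1 also tabulates, rise by 7/28 = 25% on placebo and 7/56 = 12.5% on active. Their ratio falls from 2.0 to 63/35 = 1.8.

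Over p = 10% to 30% and HR = 1.5 to 3:
- 1.3 to 3.3 of 60 subjects are added.
- The risk ratio falls from 2.71 to 2.35 at one end (p = 10%, HR 3) and from 1.38 to 1.29 at the other (p = 30%, HR 1.5).
- The risk difference shrinks by 2.6% to 8.5% of its value.

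With no drug effect both arms simply rise, for example from 20.0% to 24.3%.

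**The case against.** The strongest reply is that SAP 14 and SAP 14.1 want the same thing: tables of events that begin or worsen after the first dose. That stands. A reader might infer that the two sections give rival definitions, but they do not. SAP 14.1 assumes that the database has already applied the filter, and would agree with SAP 14 if that were so. A programmer who kept to the SAP 14 definition would still produce correct tables.

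Protocol 9.1 also gives the SAP some cover, because its AE definition refers to events after dosing starts. This may explain the wording but does not rescue it, since the start of collection is stated outright. Nor does the SAP's precedence over the protocol help: SAP 1 limits that to statistical analysis methods, and what is captured is a matter of data collection.

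A reader might go further and take the run-in vehicle as the first dose, given the broad meaning of study drug in protocol 9.1. The documents as a whole do not support this. SAP 9.3 puts the start of study treatment usually at Visit 2b, SAP 4.1 separates run-in from treatment, SAP 13.2 counts exposure from Visit 2b, and protocol 8.3.1 places the first dose of study drug there.

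A reader might also cite the summary that SAP 14 orders "by SOC, PT for SAEs; and by SOC, PT, and time of onset", for which no table title mentions onset. That is a separate gap in the table list and does not bear on this point.

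Finally, the separation is recoverable. Onset dates are documented, all AEs are listed, both Visit 2b queries precede dosing, and safety is descriptive with no inferential test. This limits the harm but does not correct the tables themselves.

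**Conclusion.** The point holds. The premise in SAP 14.1 is wrong as written and its equivalence sentence should go. Confidence is high on the conflict between the texts. It does not extend to saying that the tables will be contaminated: that depends on an eCRF build the documents do not show, and on whether programming follows SAP 14.1 or SAP 14. Either eCRF build leaves something to correct or confirm.

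The numerical effect is modest. The Step 4 figures illustrate scale and are not bounds, because the AE rates, hazard ratios and constant hazard are assumed and the CAE challenges are left out. The plan itself reports no risk ratio for AEs; the ratio is used here only to show dilution. The error should be fixed because these tables serve the primary objective and the correction is cheap.

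**What to change.** - Delete the equivalence sentence and reconcile SAP 14.1 with protocol 9.1, including the latter's mixed wording.
- Use the SAP 14 definition of a TEAE throughout, covering onset or worsening. State that first dose means the first randomised dose at Visit 2b, as SAP 4.1, 9.3 and 13.2 already imply.
- Derive a TEAE flag with a Day 1 rule. For example, a Day 1 event recorded at either Visit 2b query is pre-dose unless it later worsens, and one first reported afterwards is treatment emergent.
- Base Tables 14.3.1.1 to 14.3.1.7 on TEAEs.
- List AEs of randomised subjects from consent to first randomised dose separately.
- Confirm before lock that the eCRF holds AEs from consent. If it does not, restore them from source documents.

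The cost is SAP wording, one derived flag, one listing and an eCRF check, plus data entry if events have to be restored. No extra subjects, visits or procedures are needed.
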